### **Human Subjects Protection**

All patients with a diagnosis of meniscal or appropriate articular cartilage injury will be screened for inclusion into the study.

This study will be conducted in accordance with the current IRB-approved clinical protocol; ICH GCP Guidelines adopted by the FDA; relevant policies, requirements, and regulations of the clinical test site IRB; and applicable federal agencies.

Subjects may withdraw from the study at any time for any reason at their request. Otherwise, participants will be followed as per the protocol. Attempts will be made to collect clinical data from withdrawn subjects. There will be no replacement of subjects who withdraw from the study.

### **Subject Recruitment Methods**

The study will recruit patients who present to the Orthopaedic Sports Medicine Clinic at Wake Forest Baptist Health with symptoms requiring arthroscopic knee surgery for meniscal or articular cartilage pathology.

**Study screening and enrollment:** Potential study participants will be screened in the Orthopaedic Sports Medicine Clinic. Patients with meniscus injuries who meet the study inclusion criteria will be told about the study and will be asked if they would like to participate. The study will be described, and the requirements for study participation will be explained. Potential study participants will be encouraged to ask questions about the study and to find out what is involved in study participation. A patient information sheet will be provided to the potential subject to explain the study and used as a recruitment tool. Patients who agree to

participate will be asked to provide informed consent. No study related procedures will occur until after the informed consent is obtained. Following completion of informed consent, the study participants will be asked to complete three of the six IKDC forms including questionnaires to document demographics, current health, and subjective knee evaluations.

### **Informed Consent**

Signed informed consent will be obtained from each subject in the privacy of a clinical examination room. The study coordinator will discuss the study with patients who meet study entry criteria and will obtain consent while the patients are in the clinic following their visit with the surgeon.

### **Confidentiality and Privacy**

Confidentiality will be protected by collecting only information needed to assess study outcomes, minimizing to the fullest extent possible the collection of any information that could directly identify subjects, and maintaining all study information in a secure manner. To help ensure subject privacy and confidentiality, only a unique study identifier will appear on the data collection form. Any collected patient identifying information corresponding to the unique study identifier will be maintained on a linkage file, stored separately from the data. The linkage file will be kept secure, with access limited to designated study personnel. Following data collection, subject identifying information will be destroyed six years after closure of the study by shredding the paper documents and deleting the information from the computer files, consistent with data validation and study design, producing an anonymous analytical data set. Data access will be limited to study staff. Data and records will be kept locked and secured, with any computer data password protected. No reference to any individual participant will appear in reports, presentations, or publications that may arise from the study.

### **Data and Safety Monitoring**

The principal investigator will be responsible for the overall monitoring of the data and safety of study participants. The principal investigator will be assisted by other members of the study staff.

### **Reporting of Unanticipated Problems, Adverse Events or Deviations**

Any unanticipated problems, serious and unexpected adverse events, deviations or protocol changes will be promptly reported by the principal investigator or designated member of the research team to the IRB and Stryker Endoscopy, or appropriate government agency if appropriate.

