## Interventions and Interactions

### Evaluation Schedule Summary:

Evaluation	History / Pre-Op	Intra-Op	1 day	4 days	1 week	30 days ± 7 days	3 months ± 2 weeks	6 months ± 2 weeks	1 year ± 1 month
Patient • IKDC demographics	X								
• IKDC current health	X							X	X
• IKDC subjective knee evaluation	X					X	X	X	X
Patient phone calls • Pain scores/pain medication log			X	X					
Physician • IKDC knee history	X								
• IKDC surgical documentation form		X							
• IKDC knee examination form	X					X	X	X	X
• Document rehab duration						X	X		
Stitch Removal/ Postop Follow-up for Pain/Meds					X				

The study will include six visits: one pre-surgery visit and five post-surgery visits at one week, 30 days, three months, six months, and one year. The one week, 30 day, and three month follow-up visits coincide with the standard of care follow-up visits for patients who undergo knee arthroscopy. The six month and one year visits will be for research purposes and will not be billed to insurance providers.

Additionally, the patients will be contacted by phone at 1 and 4 days after surgery to determine their visual analog pain scores and their use of pain medications. Patients will also keep a daily log of their pain level and use of pain medications. These calls will also be used to remind patients to complete their pain diaries.

*Randomization:* A blocked randomization scheme (block size of 10) will be used to assign study participants to either single portal (Group 1) or two portals (Group 2) knee arthroscopy. Prior to surgery, the surgeon will log on to the randomization website to determine each participant's surgical group assignment. After randomization for each patient is complete, the website will document the name of the person who logged on to perform the randomization, the date and time of the log in, and the surgical group assignment for each patient. In addition, the website will document the patient's name, medical record number, and study treatment allocation. This randomization information will be forwarded to the operating room staff so that they can prepare for each study participant's surgical procedure.

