## **Outcome Measures**

### **Patient assessments:**

Patients will complete the patient-related IKDC questionnaires at each study visit except the one week visit. The IKDC is used to monitor knee symptoms, function, and activity level (1) The IKDC was developed and revised by knee experts as a knee-specific rather than a disease-specific evaluation. (1) A recent study by Van de Graff, et al demonstrated that the IKDC was better in all its measurement properties than the KOOS or the WOMAC for evaluating patients with meniscal injuries. (2)

At the pre-surgery visit, study participants will complete several components of the IKDC questionnaires including the demographic form, current health assessment form, and the subjective knee evaluation form. Patients will maintain a daily log to document their use of pain medications for the first two weeks after surgery. In addition, study participants will complete the subjective knee evaluation form at one month, three months, six months, and one year.

Patients will be contacted by phone on post-surgical days 1 and 4 to remind them to complete their daily log and to report their pain level and medication use. At each phone call and clinic visit, patients will be asked two questions: *1. What day did you feel that you had completed recovering from the surgery?* and *2. What day did you stop taking pain medicine?* Patients also will be asked these questions at the 30 day clinic visit.

If patients are unable or decline to return to clinic for follow-up, we will try to collect the patient-completed questionnaires either by telephone, by mail, or by a web-based link sent to them via a REDCap database survey at any study time point.

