### **Update to the study protocol:**

The study sponsor, Stryker, Inc. has made a business decision to no longer fund or support the continuation of the study. The study team is unaware of any serious adverse events or

unanticipated risks to patients during the course of the study. Study participants will be offered a final close-out clinical examination visit of their study knee if they have not completed the study visits. This final research visit will be at no-charge to the patient or to their insurance company.

This final study visit will consist of a brief knee exam by a member of the study team and we will measure how well the patient can bend and straighten their knee (their range of motion). We would also ask the patient to answer a short survey about their knee function and pain. This survey is the same questionnaire the patient would have completed during the study at their regular study follow-up visits (the IKDC Knee Examination Form and IKDC Current Health Assessment Form). We anticipate this visit will take approximately 15-20 minutes. We still offer patient compensation of \$10 for completion of this final study visit.

If the patient is having any other issues with their study knee, with their knee on the other side, or any other orthopaedic problems and would like to see an orthopaedic surgeon, we will offer to schedule an appointment for the patient as a regular clinical visit. However, the patient and/or their insurance provider will be charged for this appointment.

If the patient chooses not to return to the clinic for the knee exam, we will ask them to complete the final brief survey about their knee function and pain. This survey may be completed either on the telephone or by email through an electronic survey. If the patient declines to participate in this final knee exam and/or survey, we will note their decision and not contact the patient any further about this study.

Patients will be transferred to clinical management of their knee and they will be followed as part of standard clinical care by their orthopaedic surgeon in the future.

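### The plan describes no systematic collection of complications, so any comparison of safety by arm, and the close-out safety statement, rests on what staff happen to learn

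*Combined protocol and SAP*

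**What the plan says.** The section Reporting of Unanticipated Problems, Adverse Events or Deviations holds the rule for events in one sentence: "Any unanticipated problems, serious and unexpected adverse events, deviations or protocol changes will be promptly reported by the principal investigator". A designated team member may do this instead. Reports go to the IRB and the sponsor (and a government agency where appropriate). Data and Safety Monitoring adds that "The principal investigator will be responsible for the overall monitoring of the data and safety of study participants", with help from study staff. It gives no definition of an adverse event, no form and no schedule.

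The contacts are described by what they collect. The day 1 and day 4 calls are "to remind them to complete their daily log and to report their pain level and medication use". Under Patient assessments, "At each phone call and clinic visit, patients will be asked two questions": the day recovery was complete and the day pain medicine was stopped. The one-week entry in the Evaluation Schedule Summary reads "Stitch Removal/ Postop Follow-up for Pain/Meds". If a patient does not return, "we will try to collect the patient-completed questionnaires either by telephone, by mail, or by a web-based link".

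The Analytical Plan names the IKDC subjective score as primary outcome, and pain and pain medication as secondary.

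The Update to the study protocol, written when the sponsor withdrew support, begins its safety statement "The study team is unaware of any serious adverse events or" and goes on to unanticipated risks. It also says what follows "If the patient is having any other issues with their study knee, with their knee on the other side, or any other orthopaedic problems": a regular, billed clinical appointment is offered. Nothing there asks that the problem be recorded in the study.

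**The concern.** The trial randomizes patients between two surgical techniques. Its objectives concern pain, medication and function, but a reader of the results will also want to know whether complications differed. If nobody is told to ask about them, few or no recorded events could mean few events or few questions, and the two cannot be separated afterwards.

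What is noticed may also depend on the arm. The surgeon obtains the assignment from the randomization website, it is passed to operating-room staff, and no masking of follow-up staff is described. Whether an event is serious, unexpected or worth noting is then a case-by-case judgement that can be made with the assignment known.

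The close-out statement refers to serious adverse events in general, whereas the reporting rule reaches serious adverse events only if they are also unexpected. The statement is therefore wider than the rule that would feed it.

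**Working it through.** The plan states no safety figure to reproduce, so the check is mainly of the text, followed by arithmetic on what collection could show.

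**Step 1: what must be reported.** The rule has two relevant categories.
- Unanticipated problems, with no seriousness threshold.
- Adverse events that are both serious and unexpected.

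A non-serious event reaches the rule only if it is an unanticipated problem. A serious event that is a foreseeable result of arthroscopy fits neither category by its terms. The rule governs prompt reporting. No other section sets out routine recording.

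**Step 2: what each contact collects, as described.**

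| Contact | Content described | Complication item described? |
|---|---|---|
| Surgery | IKDC surgical documentation form | Not named; form not shown |
| Day 1 and day 4 calls | Pain, medication, diary reminder, two date questions | No |
| One week | Stitch removal, pain, medication, two date questions | No |
| 30 days, 3 months, 6 months, 1 year | IKDC subjective form, knee examination form and pain rating; rehabilitation duration (30 days, 3 months); current health form (6 months, 1 year) | Not named; forms not shown |
| Remote fallback | Patient-completed questionnaires | Not named; forms not shown |
| Close-out | Brief knee examination with range of motion, survey on function and pain; survey alone if the patient does not attend | Not named; forms not shown |

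**Step 3: what is analysed.** The Analytical Plan has no safety outcome and no count by arm. Confidentiality and Privacy limits collection to what is needed to assess the study outcomes. With no safety outcome listed, that limit gives a site no reason to add complication data.

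**Step 4: what collection could show.** Planned size is 55 per arm, 110 in total (Sample Size). Complication rates are not given, so 1% to 5% is an assumed range. The number enrolled at close-out is not given either, so full enrolment is assumed.
- Expected events in 110: 110 × 0.01 = 1.1, up to 110 × 0.05 = 5.5.
- Chance of at least one event in an arm, 1 − (1 − p)^55: 1 − 0.99^55 = 42%, up to 1 − 0.95^55 = 94%.
- Exact two-sided 95% upper bound for 0 of 55: 1 − 0.025^(1/55) = 6.5%. For 0 of 110: 1 − 0.025^(1/110) = 3.3%.
- Power to compare arms, n = 55 each, two-sided 5%, by the normal approximation Φ{(|p1 − p2| − 1.96·√[2p̄(1 − p̄)/n]) / √[(p1(1 − p1) + p2(1 − p2))/n]}, where p̄ is the mean of the two rates. For 5% against 10%: (0.05 − 1.96 × 0.0502)/0.0500 = −0.97, so 17%. By the same formula, 5% against 15% gives 41% and 5% against 20% gives 67%.

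The bounds apply only if every patient is asked. With unsolicited reporting, zero recorded events gives no usable upper bound.

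**The case against.** The strongest reply is that a prompt-reporting rule does not limit what a site records, and that patients are seen repeatedly. There is stitch removal at one week and a knee examination at 30 days, three months, six months and one year, and the first three visits are standard post-operative care. The current health form is completed at six months and one year. Human Subjects Protection commits the trial to ICH GCP and IRB requirements, whose content is not in the documents. Safety is not an objective, both techniques are already in use at the site, and the study is too small to test a difference.

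Much of this stands, and it rules out several stronger readings that a reader might infer:
- *That only events both serious and unexpected must be reported.* Unanticipated problems are a separate category with no seriousness threshold.
- *That a site following the plan would record almost no complications, or that no contact asks about them.* Examinations could reveal problems, and the forms are in an appendix that is not shown.
- *That the close-out statement is false or cannot be supported.* It claims only that the team is unaware, and a free examination and survey are offered to patients who have not completed their visits.
- *That the plan names reactions to pain medication as on-study risks and then ignores them.* Those entries are exclusion criteria.

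The reply does not supply a place in the protocol where complications are recorded in the same way for every patient, or counted by arm. A general commitment to GCP and a chance finding at examination do not do that.

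**Conclusion.** The point holds as a gap in collection and analysis. The protocol describes no systematic recording of adverse events or complications, gives a serious but foreseeable complication no stated reporting route, and plans no tabulation by arm. Any comparison of complications, and the close-out statement, rests on passive awareness among staff who are not described as masked.

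The effect on recorded counts cannot be calculated, because neither the true rate nor the share of events that came to notice is given. Closing the gap would yield descriptive counts only: under full enrolment, none in 55 excludes rates above 6.5%, and power is 17% for 5% against 10%. Enrolment below plan would make both weaker. The verdict also assumes that the IKDC forms contain no full complication record. If they do, the gap narrows to the missing tabulation and the reporting route. The primary outcome is unaffected. This is a change that should be made because it is cheap and because the information is hard to recover later.

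**What to change.** - **Reporting section:** require every adverse event to be recorded with its seriousness, expectedness and relatedness. Keep expedited reporting as it is.
- **Evaluation Schedule Summary:** add one fixed REDCap complication item to the existing calls and visits and to the remote fallback. It should cover infection, clot, re-operation, unplanned care for the knee and reaction to medication.
- **Close-out:** as the study is ending, put the item at least in the final examination and survey, worded to cover the whole period since surgery, and log any study-knee problem that is referred to a clinical appointment.
- **Analytical Plan:** list complications as a descriptive outcome, with counts by randomized arm, exact intervals and the number of patients asked. This also brings the item within the collection limit in Confidentiality and Privacy.
- **Update to the study protocol:** say that the absence of known events reflects unsolicited reporting.

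The cost is one REDCap form, about a minute per existing contact and an amendment to these sections, with no new staff, visits or procedures. The downsides are a little more data entry and a more cautious safety statement. An item added only at close-out relies on recall and misses patients who have finished or who decline, so its counts would be incomplete and should be reported as such.

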### **Update to the study protocol:**

The study sponsor, Stryker, Inc. has made a business decision to no longer fund or support the continuation of the study. The study team is unaware of any serious adverse events or

unanticipated risks to patients during the course of the study. Study participants will be offered a final close-out clinical examination visit of their study knee if they have not completed the study visits. This final research visit will be at no-charge to the patient or to their insurance company.

This final study visit will consist of a brief knee exam by a member of the study team and we will measure how well the patient can bend and straighten their knee (their range of motion). We would also ask the patient to answer a short survey about their knee function and pain. This survey is the same questionnaire the patient would have completed during the study at their regular study follow-up visits (the IKDC Knee Examination Form and IKDC Current Health Assessment Form). We anticipate this visit will take approximately 15-20 minutes. We still offer patient compensation of \$10 for completion of this final study visit.

If the patient is having any other issues with their study knee, with their knee on the other side, or any other orthopaedic problems and would like to see an orthopaedic surgeon, we will offer to schedule an appointment for the patient as a regular clinical visit. However, the patient and/or their insurance provider will be charged for this appointment.

If the patient chooses not to return to the clinic for the knee exam, we will ask them to complete the final brief survey about their knee function and pain. This survey may be completed either on the telephone or by email through an electronic survey. If the patient declines to participate in this final knee exam and/or survey, we will note their decision and not contact the patient any further about this study.

Patients will be transferred to clinical management of their knee and they will be followed as part of standard clinical care by their orthopaedic surgeon in the future.

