### **Physician assessments:**

The principal investigator will complete the IKDC knee history form, surgical documentation form and knee examination form at baseline. At 30 days, three months, six months, and one year the physician assistant or other designee will complete the knee examination form. Additionally, the rehabilitation duration will be noted at the 30 days and three month visit per patient report.

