### **Patient Retention**

Every effort will be made to retain patients in the study to ensure complete data collection. During the study consent process, potential study participants will be educated regarding the importance of full participation in all visits. Study participants will be called at 1 day and 4 days after surgery. At these calls, patients also will be reminded of their upcoming appointments. Patients will also be reminded about their follow-up visits at all clinic visits. Patients will also be given an information packet about the study. This packet will include a list of the dates for the phone calls and the dates of their follow-up clinic visits.

If patients are unable or decline to return to clinic for follow-up, we will try to collect the patient-completed questionnaires either by telephone, by mail, or a web-based link sent to them via a REDCap database survey at any study time point.

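### The close-out text does not name the primary-outcome questionnaire among the forms to be collected

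*Combined protocol and SAP*

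**What the plan says.** The section Update to the study protocol closes the study after the sponsor withdrew support: "Study participants will be offered a final close-out clinical examination visit of their study knee if they have not completed the study visits". The visit has two parts. One is a brief knee examination with range of motion, done by a study team member. The other is a patient survey: "We would also ask the patient to answer a short survey about their knee function and pain". The text continues: "This survey is the same questionnaire the patient would have completed during the study at their regular study follow-up visits", and a parenthesis then gives the forms as "the IKDC Knee Examination Form and IKDC Current Health Assessment Form". For anyone who does not come to clinic: "This survey may be completed either on the telephone or by email through an electronic survey".

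Elsewhere the plan assigns the forms as follows.

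- The evaluation schedule lists the knee examination form under Physician. For the follow-up visits, Physician assessments says "the physician assistant or other designee will complete the knee examination form".
- The schedule and Patient assessments make the Subjective Knee Evaluation Form due from the patient at 30 days, 3 months, 6 months and 1 year.
- The Analytical Plan makes the score on that form the primary outcome.
- Objectives states the IKDC hypothesis at six months and one year.
- Remote collection during the study is limited to what patients fill in themselves: "we will try to collect the patient-completed questionnaires either by telephone, by mail", or by web link.

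**The concern.** The description of the close-out survey and the forms given for it do not agree. A form filled in by clinical staff is not a questionnaire the patient would have completed at follow-up, and it cannot serve as a telephone or electronic patient survey. The form that best fits the description, and the one the primary analysis needs, is not mentioned anywhere in the section.

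This matters because the section is the working instruction for the last planned research contact, and participants who decline it will not be contacted again about the study. If the visit packet or electronic survey is built from the forms as named, a 6-month or 1-year primary-outcome score that could have been obtained at that contact is lost for good. Early closure already reduces the number of such scores, so each one that remains obtainable is worth collecting.

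**Working it through.** The check is mainly textual. The plan gives no figure on this point to reproduce.

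**1. The three forms used at follow-up, side by side** (from the evaluation schedule, Patient assessments, Physician assessments and the Analytical Plan)

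| IKDC form | Completed by | Due after surgery | Gives primary-outcome score | Named at close-out |
|---|---|---|---|---|
| Subjective Knee Evaluation | Patient | 30 days, 3 months, 6 months, 1 year | Yes | No |
| Current Health | Patient | 6 months, 1 year (schedule) | No | Yes |
| Knee Examination | Clinical staff | 30 days, 3 months, 6 months, 1 year | No | Yes |

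The Current Health row has a small ambiguity of its own. Patient assessments opens with "Patients will complete the patient-related IKDC questionnaires at each study visit except the one week visit", which read literally would add 30 days and 3 months. The finding does not depend on this.

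**2. Two readings of the parenthesis**

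- *Both forms make up the survey.* The Knee Examination Form then conflicts with the survey being answered by the patient, being the regular follow-up questionnaire, and being open to telephone or electronic completion.
- *The parenthesis loosely covers the whole visit,* with the Knee Examination Form for the examination and the Current Health form for the survey. The clinician-form conflict goes away, but the survey is then only part of what the patient completed at follow-up.

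On both readings, named forms that give a primary-outcome score: 0 of 2.

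**3. Which form the description fits**

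The Analytical Plan explains the Subjective form's score in terms of daily activities, sports and knee symptoms. That matches a survey of function and pain, so the Subjective form may well have been meant. The questionnaire items are not reproduced, so this cannot be confirmed.

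**4. What one close-out contact could supply**

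The hypothesis has 2 IKDC time points. For a participant still in follow-up:

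- before the 6-month visit, 2 of 2 are outstanding;
- after it, 1 of 2 (the 1-year score) is outstanding.

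The schedule's windows are 6 months ± 2 weeks and 1 year ± 1 month. The first closes at 6 months + 2 weeks, about 6.5 months. The second opens at 12 − 1 = 11 months. The gap is about 11 − 6.5 = 4.5 months, so the windows do not overlap. One contact can fill at most 1 time point, and fills 0 if it falls outside both windows.

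**5. Time cost of adding the form**

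The Analytical Plan gives about 5 minutes for the form, and the close-out text gives 15–20 minutes for the visit. 5/20 = 25% and 5/15 = 33%, if the form is not already counted in that estimate.

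**The case against.** The strongest reply is that most of the missing follow-up comes from the sponsor's decision, not from the parenthesis. Time points outstanding at closure are outstanding whichever form is named. **This stands as a limit on size.** The wording itself can cost only the scores from contacts that fall inside a window, and the count of outstanding time points is an upper bound.

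Second, on the loose reading little is contradicted: the examination is described separately, only the survey goes to telephone or email, and the Current Health form is a genuine patient form. **This stands in part.** It removes the clinician-form conflict but leaves the primary-outcome form unnamed.

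Third, the form may simply be misnamed, and staff who follow the description would collect it. **This also stands.** The documents show that the form is not named; they do not show that it was not collected.

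Fourth, the close-out text does not say its data will enter the primary analysis, so the authors need only clarify what they meant. Clarification is indeed the minimum. But the form is already in the study and takes about five minutes, and without it no in-window score can be kept, so there is good reason to go further and name it.

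**Conclusion.** The concern holds. The close-out text identifies the patient survey by two forms, neither of which gives the primary outcome, and one of which is not a patient form.

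Whether any data are lost depends on staff following the named forms rather than the description. If they do, the loss is at most one hypothesis time point per participant contacted. Scores from completed visits are unaffected, including the 6-month score of anyone closed out after that visit. The documents do not say how many participants were enrolled or still in follow-up at closure, so no patient count or loss of power can be stated.

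This should be fixed, since it governs the last chance to collect the primary outcome. The omission itself is certain; its consequence is conditional.

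**What to change.** Reconcile the close-out section with the evaluation schedule, Patient assessments, Physician assessments and the Analytical Plan:

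- Name the IKDC Subjective Knee Evaluation Form as the patient survey, whether completed in clinic, by telephone or electronically. The Current Health form can stay alongside it.
- Tie the Knee Examination Form to the in-person examination only.
- Record the completion date, and count a close-out score as a 6-month or 1-year value only if it falls within the existing window for that visit. Scores outside both windows can be reported as function at exit, but cannot stand in for either visit.

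The cost is a small change to the close-out text, with no new instrument, plus the five minutes per patient worked out above. Some of the scores collected will fall outside the windows and will not serve the primary comparison.
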